**LIST OF ABBREVIATIONS AND RELEVANT DEFINITIONS**

ABR	General Assessment and Registration form (ABR form), the application form that is required for submission to the accredited Ethics Committee; in Dutch: Algemeen Beoordelings- en Registratieformulier (ABR-formulier)
AE	Adverse Event
AR	Adverse Reaction
CA	Competent Authority
CCMO	Central Committee on Research Involving Human Subjects; in Dutch: Centrale Commissie Mensgebonden Onderzoek
CV	Curriculum Vitae
DSMB	Data Safety Monitoring Board
EU	European Union
EudraCT	European drug regulatory affairs Clinical Trials
EULAR	European League Against Rheumatism
GCP	Good Clinical Practice
GDPR	General Data Protection Regulation; in Dutch: Algemene Verordening Gegevensbescherming (AVG)
IB	Investigator's Brochure
IC	Informed Consent
IMP	Investigational Medicinal Product
IMPD	Investigational Medicinal Product Dossier
KJD	Knee Joint Distraction
KP	Knee Prosthesis
METC	Medical research ethics committee (MREC); in Dutch: medisch-ethische toetsingscommissie (METC)
(S)AE	(Serious) Adverse Event
SPC	Summary of Product Characteristics; in Dutch: officiële productinformatie IB1-tekst
Sponsor	The sponsor is the party that commissions the organisation or performance of the research, for example a pharmaceutical company, academic hospital, scientific organisation or investigator. A party that provides funding for a study but does not commission it is not regarded as the sponsor, but referred to as a subsidising party.
StWP	State of knowledge and clinical practice
SUSAR	Suspected Unexpected Serious Adverse Reaction

TKP	Total Knee Prosthesis
UKP	Unicompartmental Knee Prosthesis
UAVG	Dutch Act on Implementation of the General Data Protection Regulation; in Dutch: Uitvoeringswet AVG
VAS	Visual Analogue Scale
WMO	Medical Research Involving Human Subjects Act; in Dutch: Wet Medisch- wetenschappelijk Onderzoek met Mensen

## SUMMARY

**Rationale:** For relatively young ( $\leq 65$  year) patients with severe knee osteoarthritis (OA) with persistent pain, insufficiently responding to conservative therapy and joint preserving surgery ('end-stage knee OA') a knee prosthesis (KP) is currently the most commonly used treatment. When a first prosthesis is placed at a young age, patients often need revision surgery later in life. Revision surgery is complex, costly, and accompanied by multiple complications. The increasing life expectancy, focus on patient empowerment, and the wish to stay active and independent up to high age, is anticipated to further increase the number of revision surgeries. As such, preventing revisions surgery is key. When a first prosthesis is placed after the age of 65, data show that the need for revision surgery becomes significantly lower.

Knee joint distraction (KJD) is a joint preserving treatment that significantly postpones the need for a primary knee prosthesis (up to  $\sim 10$  years in 50% of cases). KJD is proven to be effective in reducing pain and stiffness and improving function, although effects seem slightly less compared to a knee prosthesis. As assessed by 'Zorg Instituut Nederland', KJD is promising but the current evidence still too limited and thus not yet suitable for reimbursement. Even in case KJD is less effective, if this is clinically acceptable (non-inferior), the reduced chance for burdensome revision surgery might still make it a treatment of choice.

With respect to the GODIVA-bone add-on study: i) Reaching a well-balanced decision made by patient and surgeon together (shared decision-making) on whether to be treated with knee distraction or not, based on a scientifically justified chance for success of knee distraction treatment, is key for future implementation of knee distraction. ii) A more in-depth insight in the relationship between peri-articular bone changes and improvement in pain perception and cartilage repair may add to development and/or improvement of new and existing treatment strategies for knee osteoarthritis directed towards bone.

**Objective:** To determine whether KJD is non-inferior on patient reported effectiveness as compared to a KP (i.e. usual care) for relatively young patients with end-stage knee OA. In the GODIVA bone substudy, the primary objective is to predict the benefit from knee distraction treatment by peri-articular bone characteristics. The secondary objective of the substudy is understanding the change in peri-articular bone in relation to the benefit from knee distraction treatment (pain relief and cartilage repair) by expanding the pre-treatment data with follow-up data.

**Study design:** Pragmatic, open, randomized, multi-centre, non-inferiority trial with 24 months follow-up.

**Study population:** 1,200 knee OA patients  $\leq 65$  year of age, indicated for a KP will be randomized (1:1) to KJD or KP. For the GODIVA-bone substudy: 200 patients from the 600 patients randomised to treatment with knee distraction in the GODIVA trial will be included.

**Intervention (if applicable):** KP is indicated and surgically implanted according to regular clinical practice (can be a total- or unicompartmental KP, in line with local practice in consultation with the patient and conform the national guideline by Dutch orthopaedic society (NOV)). KJD treatment is performed according to the current approved concept NOV recommendations for clinical practice.

**Main study parameters/endpoints:** Primary endpoint: Western Ontario and McMaster Universities Arthritis Index (WOMAC) total score. Main secondary outcomes: WOMAC/KOOS Pain, stiffness, and physical function sub-scores, quality of life (EQ-5D, SF-36), radiographic joint space width (KJD only) as a surrogate for cartilage tissue repair; adverse events, and productivity and healthcare cost. All assessed over 24 months.

For the GODIVA-bone sub-study the main parameters are MRI, CT, and DEXA image markers and blood and urine biochemical markers at baseline and 24 months.

**Nature and extent of the burden and risks associated with participation, benefit and group relatedness:** The benefit of a KP over KJD might be the swifter and slightly better clinical effect of treatment although at the expense of the original joint and with the higher risk of revision surgery later in life. The benefit of the KJD over a KP is that the original joint is preserved with the chance of postponing placement of a KP and decreasing the chance of revision surgery later in life, although with the burden of a 6-week distraction period with the chance of skin pin-tract infections, and possibly a slightly (non-clinically relevant) lesser clinical benefit.

In both arms, at 7 moments questionnaires must be filled out without the need of a clinic visit. At baseline for both treatments, and in case of KJD treatment additionally at 24 months a clinic visit takes place (the latter for a study specific x-ray) in addition to the typically 4 clinic visits performed in regular practice. In both arms a comparable number of knee radiographs is made in regular care and for KJD the 24 months study specific x-ray will be made.

In both arms the chance of failure is <5% in the first year after treatment. Failure can be due to multiple reasons, mostly persisting pain, leading to either revision surgery in case of a KP or placement of a first KP in case of KJD. Additionally, there is a chance of infection in both arms. In case of KJD these are primarily superficial skin pin tract infections, in generally successfully treatable with oral antibiotics. In both arms a small chance for deeper infections up to osteomyelitis are seen, needing i.v. antibiotics and/or nettoyage or even removal of the frame in case of KJD or early revision surgery in case of KP. Rehabilitation after the intervention(period) is similar for both treatment arms.

Patients randomised to knee distraction in the GODIVA trial are asked to participate in this GODIVA-bone add-on study. In case of consent, the burden will be a knee-MRI, knee-CT, and DEXA scan at pre-treatment and 2 years post-treatment, which will take two times an 60-120 min extra out-patient visit time. These image techniques are considered minimally

[figure not shown]
invasive with CT and DEXA with radiation exposure. Additionally, a vena puncture for 2 times 7 cc blood samples (serum and plasma) at both timepoints provides a minimal risk. The urine samples are considered riskless. There is no direct benefit for the patient.

## 1. INTRODUCTION AND RATIONALE

Knee osteoarthritis (OA) is a degenerative joint disease characterized by articular cartilage degeneration, periarticular bone changes, and soft tissue impairment causing pain, stiffness, and functional limitations, and considerable loss of quality of life (1,2). In the Netherlands, yearly almost 30,000 (total and unicompartmental) knee prostheses (KP) are placed for patients not sufficiently responding to conservative therapy or joint preserving surgery ('end-stage knee OA') (3).

About 30% of KP's are implanted under the age of 65. These patients have a significantly higher risk of revision surgery later in life, i.e., up to 35% and 20% in men and women, respectively in the age category 50-55 (4). When a first prosthesis is implanted after the age of 65, the need for revision surgery significantly decreases (see figure 1).

[figure not shown]
*Lancet 2017; 389: 1424-30*

*Figure 1 Lifetime revision rate of knee replacement*

Revision surgery is complex, costly, and accompanied by multiple complications (5-7). With the increasing life expectancy, focus on patient empowerment, and the wish to stay active and independent up to high age, this problem is anticipated to further increase. Treatments that can postpone a KP are therefore desired.

Knee-Joint-Distracton (KJD) is such a treatment and uniquely demonstrates cartilage tissue repair (8,9) as well as amelioration of complaints. KJD places the two bony ends of the knee joint at a distance of about 5 mm for a period of about 6 weeks according to prescribed procedures as described and advised by the NOV (the Dutch orthopaedic society), see appendix S.

[figure not shown]
Several prospective studies and two RCTs have been performed. All KJD treated patients reached a ‘patient acceptable symptom state’ based on KOOS/WOMAC questionnaire domains and > 85% reached response according to modified OMERACT-OARSI criteria (own analysis) (8) see also table/figure above.

The mechanism behind its effect is still largely unknown but thought to be related to the absence of mechanical stress on the joint combined with intra-articular biochemical changes which allow damaged cartilage to repair itself (10).

Based on the data from previous research and preliminary combined analyses, bone parameters are considered key in response to knee distraction treatment. (Spil W et al., Ann Rheum Dis 2013;72,) (Black A, J Orthop 2022;32,) (Curry Z et al. Menopause 2022;29,);

Recently Zorg instituut Nederland (ZiN) performed an evaluation of the ‘state of knowledge and clinical practice (StWP)’ for KJD for the treatment of knee-OA indicated for a KP at a younger age (65 years). It was concluded that KJD is a promising treatment, but that the current evidence regarding this treatment is still insufficient for KJD to be eligible for reimbursement. Their judgement was mainly based on a small (n=20:40 patients) RCT comparing KJD to a total KP performed by our group (8). Patients showed no statistically

significant difference in patient reported efficacy outcomes between KJD and TKP, but the results seem to indicate that compared to KP, KJD is slightly less effective. See also table/figure below

This RCT was a comparison between KJD and a total KP. Roughly, there are two types of a knee prosthesis, a unicompartmental or total knee prosthesis. A total knee-prosthesis (TKP) has shown to be effective in reducing pain and regaining function. The average quality of life (utility) increases from 0.6 (preoperatively) to 0.85, indicating a substantial overall effectiveness (3). However, 20% of people are not satisfied and difficulties with kneeling and persisting pain commonly occur (4,6,7). Moreover, specifically when placed at a young age (<65 years), a significant number of patients will need revision surgery. Unicompartmental knee prostheses (UKP) are presently used in ~13% of all patients receiving a KP and specifically (in ~25%) in younger patients. Although, overall long-term results regarding revision rates are still less satisfactory, this may be due to the originally limited experience with the procedure. In centers implanting UKPs in higher numbers, UKP provides better long-term results that are comparable to TKP (11,12). Therefore, this type of KP is also suitable for younger patients.

## 2. OBJECTIVES

### Primary Objective:

- To determine whether KJD is non-inferior to usual care (KP) regarding patient reported effectiveness as measured using the Western Ontario and McMaster Universities Arthritis Index (WOMAC) total score (0-100; higher is better), over 2 years.

### Secondary Objective(s):

- To determine whether KJD is non-inferior to usual care (KP) on patient reported effectiveness regarding secondary patient reported outcomes (e.g. WOMAC subscores for pain, disabilities and stiffness, quality of life) over 2 years.
- For KJD only: To determine the change in radiographic joint space width over 2 years compared to baseline (i.e. before KJD treatment) as a surrogate marker for cartilage tissue repair.
- To describe and compare adverse events between KJD and KP (including reoperations) over 2 years.
- In the **GODIVA-bone substudy**: to predict the beneficial effects of knee distraction treatment for patients with knee osteoarthritis, based on peri-articular bone characteristics.
- In the **GODIVA-bone substudy**: to elucidate the relationship between periarticular bone changes (pre- and 2 years post-treatment) and improvement in pain perception and cartilage repair.

### Tertiary Objective:

- To describe and compare productivity and healthcare costs between KJD and KP over 2 years.
- To compare knee flexion over time

### 3. STUDY DESIGN

Pragmatic, open, randomized, multi-centre, non-inferiority trial. 1,200 patients who satisfy the eligibility criteria will be randomized 1:1 to receive KJD or KP as initial treatment. These patients will be followed for 24 months. Both strategies will be implemented in regular care in participating centers taking current NOV practice recommendations for both treatments into account. In general study visits coincide with regular care although some visits are specific for the study and most outcome information is collected digitally via e-mail. Patients will be included over a period of 2 years.

**GODIVA-bone substudy:** The GODIVA trial provides an ideal platform to add specific measurements for bone (imaging and biochemical) before and two years after treatment to a subset of patients who will be treated with knee distraction (n=200).

At least 7-10 participating centers (together scheduled for over 200 knee distractions in the GODIVA trial) have been identified based on the availability of (access to) the right imaging equipment enabling the proper image acquisition and infrastructure for blood sampling and processing.

## 4. STUDY POPULATION

### 4.1 Population (base)

Patients with knee OA considered for a KP according to regular clinical practice in line with NOV guidelines / recommendations without restrictions to undergo KJD.

Patients are treated in 14 orthopaedic centres according to local practice and expertise in line with NOV recommendations. All consecutive patients visiting the centres' outpatient clinics considered for KP and eligible for KJD are asked to participate.

**GODIVA-bone substudy:** In a selection of the participating centers all consecutive patients randomized to the knee distraction arm are asked to participate (up to 200 inclusions in total) in the GODIVA-bone substudy.

Below in-/exclusion for the study are in line with NOV guidelines for KP as well as the NOV (concept) recommendations for KJD in clinical practice (see appendix S).

### 4.2 Inclusion criteria

To be eligible to participate in this study, a subject must meet all the following criteria:

- Clinical diagnosis of knee OA
- Age  $\leq 65$  years and  $\geq 18$  years
- Persistent, refractory pain, insufficiently responding to conservative or previous surgical therapy
- Structural OA joint damage, indicated by a K&L grade of at least 2 as determined by the orthopedic surgeon in line with NOV recommendations.
- Able to wear an external fixator and care for it for 6 weeks
- Accepting that the maximal effect of KJD is not present directly after removal of the frame but may take months after frame removal
- Sufficient joint stability (according to the orthopedic surgeon's judgement)
- Flexion ( $>100$  degrees) and extension range ( $<10$  degrees)
- Weight and BMI  $<120$  kg and  $<35$  kg/m^2, respectively
- Sufficient understanding of the Dutch language
- Signed informed consent

### 4.3 Exclusion criteria

A potential subject who meets any of the following criteria will be excluded from participation in this study:

- Primary patella-femoral knee osteoarthritis
- Surgical intervention in last 6 months
- Leg-axis deviation  $> 10$  degrees (as determined by the orthopedic surgeon)
- Serious osteopenia making placing bone-pins and wearing a frame into a risk (according to the orthopedic surgeon's judgement)
- Coagulation problems making occurrence of thrombosis or embolies into a risk (according to the orthopedic surgeon's judgement)
- Existing endoprosthesis at any other joint (e.g. hip or contralateral knee) to prevent infection of existing prosthesis
- History or presence of joint infection/inflammation
- Hypersensitivity to antibiotics
- Presence of systemic inflammatory disease, like rheumatoid arthritis

- Extra for **the GODIVA-bone substudy**: Inability to undergo a knee-MRI or knee-CT and DEXA according to the local enforced criteria in regular health care.

#### 4.4 Sample size calculation

In the recently performed 'StWP' evaluation of KJD by 'Zorg Instituut Nederland (ZiN)' a non-inferiority limit for the 'crucial' endpoint of total WOMAC score at 2 years (the primary endpoint here) was defined at 15.

Assuming a 'true' difference in total WOMAC score of 12 points in favor of KP based on previous (pilot) data with an SD of 15 (14), 527 patients need to be recruited into each arm to obtain 90% power (2.5% one-sided significance) to demonstrate 'non-inferiority' (calculated using the power procedure in SAS 9.4). To account for missing data and loss to follow-up, we increase the sample size with ~15% and will include 600 patients per group.

**Sample size considerations for the GODIVA-bone substudy:** The response outcomes to use for the prediction models have an occurrence between ~30% and ~50%, indicating that with the 200 patients included (2/3 responder, i.e. 134 patients) we will have between 60 and 100 events for our analysis (between 40 and 67 for model development). Based on general rule of thumb, where at least 5-10 events per variable studies are needed we will have room for maximally 13 predictive parameters. To adhere to this, when needed, we will use data reduction techniques (e.g. principal component analysis or other feature reduction/selection techniques) or analysis techniques, suitable for sparse data, like penalized regression techniques to be defined in the SAP. For the secondary aim (explorative) we will relate changes in bone parameters to changes in pain (WOMAC pain) and cartilage tissue repair (radiographic joint space width increase) over a period of two years. The same parameters as explored in the predictive analysis as well as changes therein will be used as independent variables in this analysis.

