### 8.1.4 Other study parameters (if applicable)

General demographics such as age, gender, BMI as well as clinical parameters such as previous surgery (Appendix P) at the index knee and current indication for type of KP (TKP or UKP) will be evaluated. Some of these are well known prognostic factors for the prognosis of knee OA and/or effectiveness of KP or KJD treatment (16) and as such may act as treatment effect modifiers which will be explored.

The (limited) preference patients (Appendix H) participating in the study may have for one of the treatments will be measured and the effect on treatment effectiveness explored. OA severity (measured by the Charnley score, Appendix I) and patients general health (ASA classification, Appendix J) will also be measured as a descriptive variable as well as to make future matching of patients to patients from the Dutch national registration of orthopaedic implants (LROI) possible (outside the scope of this proposal).

Finally, the Pain-Detect Questionnaire (Appendix K) will be assessed at baseline to identify neuropathic components of a patients' pain, which may also be relevant with regard to patients prognosis and treatment effects.

**For the GODIVA-bone substudy:** Evaluation of imaging markers will be performed in three stages.

In the first stage, bone parameters will be scored, as scoring would be easily feasible to apply in clinical practice for the assessment of suitability for KD treatment. From radiographs, subchondral bone structure, and osteophytes will be scored automatically, which can be done with KOALA software (ImageBiopsyLab; [Jansen M et al. Osteoarthr Imag 2022;100018]). From DEXA scans, the T- and Z-score output

will be used [Ishii Y et al. Open Orthop J 2016;10,]. From CTs, subchondral bone density, cysts and osteophytes will be scored using the OACT scoring system [Gielis W et al. J Pers Med 2020;11,]. From MRI scans, bone marrow lesions (BMLs) and cysts will be scored with the WOMBS scoring method [Roemer F et al. Osteoarthr Cartil 2016;24,].

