### 8.3 Study procedures

The following study assessments will be performed according to the schedule below.  
See appendices B-P for questionnaires.

	Screening/ Baseline	Pre- surg ery	Surg	Post-surgery								ET
				3w	6w	2m	5 m	8 m	12 m	24 m		
Weeks/ months	-2m (max)		0	+/- 1w	+/- 1w	+/- 2w	+/- 1m	+/- 1m	+/- 1m	+/- 2m		
Visits	V0			v1		v2	v3	v4	v5	v6		
General												
Informed consent	x											
In- and exclusion criteria	x											
Demographics/ characteristics	x											
Surgical medical history index knee	x											
Randomization		x										
Surgical treatment												
Knee prosthesis (KP) or Knee Joint Distraction (KJD) frame placement			x									
Removal KJD frame					x							
Questionnaires												
Pain Detect (neuropathic pain)	x											
KOOS (incl. pain medication)	x						x	x	x	x		
SF36	x								x	x		
EQ5D-5L	x			x		x	x	x	x	x		
NRS-Pain	x			x		x	x	x	x	x		
Patient Acceptable Symptom State	x						x		x	x		
NRS-Patient satisfaction							x		x	x		
Medical Consumption Quest. (MCQ)	x					x	x		x	x		
Productivity Cost Quest. (PCQ)	x					x	x		x	x		
Other												
Radiographic Joint space width (follow-up for KJD only) in mm **	x								x	x		
Adverse events/ additional surgical procedures *				x	x	x	x	x	x	x		
Knee flexion*	x			x	x	x	x	x	x	x		
Phone call											x	
GODIVA-bone substudy#												
Informed consent substudy	x											
In- and exclusion criteria substudy	x											
Image and biochemical markers for bone ##		x								x		

\* Adverse events / additional surgical procedures and knee flexion are specifically registered during regular care visits in a standardized way (continuous registration) so no study specific visits are planned for these measurements. Knee flexion is also measured at the baseline visit

\*\* Radiographs of the knee (according to KIDA protocol) for follow-up will only be taken after KJD (baseline X-ray for both KJD and KP). Only the 24-month x-ray is extra compared to KJD treatment in regular care according to preliminary NOV recommendations. Visits depicted in bold are study-specific clinic visits.

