#### **With respect to the GODIVA-bone substudy;**

Development of prediction model: A multivariable prediction model will be developed to predict the response after KD treatment. Separate analyses for clinical success (defined as 15 points improvement in WOMAC pain), radiographic success (any increase in minimal JSW (>0 mm)) and success both clinically and radiographically will be performed. Also, more stringent cut-offs will be used e.g. based on the minimal detectable change. Model building will be performed stepwise starting with the predictive parameters that are more easily accessible in regular clinical practice (e.g. demographics and scores of bone parameters) as predictors, and thereafter the more demanding parameters (i.e. continuous scores, parameters derived from more sophisticated imaging modalities) are added. The total set of parameters to use as predictors in multivariable modelling will be decided based on initial findings (e.g. analysis during the third stage as described above), external findings from e.g. literature as well as clinical and biological expertise.

The modelling technique to use will be determined by experimentation, predictive performance, robustness, and 'explainability' of models and will be decided in discussion with clinicians, epidemiologists, data scientists and patients to ensure that the resulting models are statistically adequate and clinically useful.

All prediction models will be developed and externally validated (e.g. by using 2/3 of the data for development (including cross-validation for internal validation) and the remaining data as external validation data).

All data handling procedures and analyses to be performed, including the handling of missing data, specific features to be developed, and algorithms to use will be described in

a Statistical Analysis Plan (SAP) before 'database lock'. This SAP will be finalized in cooperation with the methodologists from our department and from the Julius Center with which we cooperate in several other projects. Models will be developed and reported according to the TRIPOD criteria [Collins G et al. BMC Medicine 2015;13,].

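### A radiograph-and-demographics prediction model could be validated in the roughly 400 KJD patients outside the GODIVA-bone substudy, but the protocol names no such use and sizes all models on 200

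*Protocol*

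**What the plan says.** **Sample for the models.** The Summary sets the substudy at one third of the distraction arm: "200 patients from the 600 patients randomised to treatment with knee distraction in the GODIVA trial will be included". In section 4.4 the event count for the prediction models rests on that number: "with the 200 patients included (2/3 responder, i.e. 134 patients) we will have between 60 and 100 events for our analysis". The same paragraph gives 40 to 67 events for development and room for at most 13 parameters. Section 10.3 would develop and validate all models, for example with two thirds of the data for development (with cross-validation) and the rest as what it calls external validation.

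**Predictors.** Section 10.3 describes the order of work: "Model building will be performed stepwise starting with the predictive parameters that are more easily accessible in regular clinical practice", with demographics and bone scores given as examples. Section 8.1.4 lists the first-stage scores. One item is radiographic: "From radiographs, subchondral bone structure, and osteophytes will be scored automatically, which can be done with KOALA software". The others are DEXA T- and Z-scores, CT scores and MRI scores. In the second stage, subchondral bone density and osteophyte size are also measured from radiographs with KIDA.

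**Who has which data.** Section 8.3 states: "Radiographs of the knee (according to KIDA protocol) for follow-up will only be taken after KJD (baseline X-ray for both KJD and KP"). The schedule there gives every KJD patient a baseline radiograph, follow-up radiographs at 12 and 24 months, and KOOS (hence WOMAC pain) at baseline and 24 months. MRI, CT, DEXA, blood and urine are collected in substudy participants only.

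**Outcomes.** Section 10.3 defines clinical success as a 15-point improvement in WOMAC pain, radiographic success as any increase in minimal joint space width, and a combination of the two.

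**The concern.** The Summary presents the substudy as a basis for shared decisions between patient and surgeon, and section 8.1.4 favours scores that are easy to apply in practice. A model built from demographics, clinical data and a plain radiograph is the version most clinics could use. It is also the one version for which the substudy's special measurements are not needed.

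Under the stated sizing, that model would be developed in about 134 patients and tested in about 66. Some 400 further KJD patients are scheduled to have the same predictors and outcomes, yet no section assigns them a role in developing or validating it. At stake is the precision with which the most practical model is validated. The main trial's endpoint, its safety data and the validity of its stated analyses are not affected.

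**Working it through.** **1. The plan's own figures.** Inputs: 200 patients; outcomes that "have an occurrence between ~30% and ~50" per cent of patients; a two-thirds development share; 5 to 10 events per variable.

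- Events: 200 × 0.30 = 60 and 200 × 0.50 = 100, as stated.
- Development: 134 × 0.30 = 40.2 and 134 × 0.50 = 67, as stated. The 134 is therefore the two-thirds development share, although the text in brackets calls it responders.
- Parameters: 67 / 5 = 13, as stated. This is the most favourable corner; the least favourable is 40 / 10 = 4.
- Held-out third: 200 − 134 = 66 patients, with 66 × 0.30 ≈ 20 to 66 × 0.50 = 33 events.

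**2. Which data exist outside the substudy** (sections 8.1.2, 8.1.4, 8.3)

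| Item | All 600 KJD | Substudy 200 only |
|---|---|---|
| Demographics, clinical data | yes | |
| Baseline radiograph (KOALA, KIDA parameters) | yes | |
| WOMAC pain, baseline and 24 months | yes | |
| Joint space width, baseline and 24 months | yes | |
| MRI, CT, DEXA, blood, urine | | yes |

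Patients outside the substudy: 600 − 200 = 400. The protocol's loss allowance is "we increase the sample size with ~15% and will include 600 patients per group". Taking 15% loss as an assumption, 400 × 0.85 = 340.

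**3. Precision of validation.** The protocol gives no expected AUC, so A = 0.70 is assumed. The Hanley-McNeil variance for n₁ responders and n₀ non-responders is

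Var = [A(1 − A) + (n₁ − 1)(q₁ − A²) + (n₀ − 1)(q₂ − A²)] / (n₁n₀), with q₁ = A/(2 − A) and q₂ = 2A²/(1 + A).

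At A = 0.70: q₁ = 0.5385, q₂ = 0.5765, A² = 0.49.

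Example, 66 patients with 20 events: [0.21 + 19 × 0.0485 + 45 × 0.0865] / (20 × 46) = 5.02 / 920 = 0.00546. The standard error is 0.0739 and the half-width 1.96 × 0.0739 = 0.145.

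| Validation set | Events (30% / 50%) | 95% half-width | Lower limit |
|---|---|---|---|
| 66 | 20 / 33 | 0.145 / 0.126 | 0.555 / 0.574 |
| 400 | 120 / 200 | 0.059 / 0.051 | 0.641 / 0.649 |
| 340 | 102 / 170 | 0.064 / 0.055 | 0.636 / 0.645 |

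The 66 carries no loss here, so the last row compares conservatively.

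**4. Range for the assumed AUC** (same formula, 30% / 50% response)

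| AUC | Half-width, n = 66 | Half-width, n = 400 |
|---|---|---|
| 0.60 | 0.153 / 0.137 | 0.062 / 0.055 |
| 0.70 | 0.145 / 0.126 | 0.059 / 0.051 |
| 0.80 | 0.127 / 0.108 | 0.051 / 0.043 |

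Across this range the larger set narrows the interval by a factor of about 2.5. At an AUC of 0.60 the interval from 66 patients would include 0.50 (0.60 − 0.137 = 0.463); at 0.70 it does not.

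**5. Effect on development.** If validation takes place outside the substudy, this model needs no split and can be developed in all 200: 60 to 100 events in place of 40 to 67. That allows 12 to 20 parameters at 5 events per variable (60 / 5, 100 / 5) or 6 to 10 at 10 per variable, against 8 to 13 or 4 to 6 with the split.

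**The case against.** The strongest reply has five parts.

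- **The first modelling step is not defined as radiographic.** A reader might infer that the protocol's first-step model consists of demographics and radiographic scores and is wrongly confined to 200. The text does not support that. The first-stage scores in section 8.1.4 include DEXA, CT and MRI scores, so a first step using all of them cannot be fitted in 600. This stands, and the point is therefore restricted to a model limited to demographics, clinical data and radiographic parameters.
- **Nothing says that the other 400 are discarded.** That too would be an inference, from silence. Section 8.1.4 speaks of available baseline images and of integration with the main trial where relevant, section 10.3 introduces the split as an example, and the 400 serve in the main trial's analyses. This stands; what can be said is that no use for such a model is named.
- **Detail is left to the SAP.** Section 10.3 defers data handling, features and algorithms, and the SAP may add this use. That is a fair reply, but section 4.4 already fixes the sample on which the models are sized, and that is the choice addressed here.
- **A common sample is sensible.** Comparing the added value of each modality calls for the same patients throughout. This stands, and the change below keeps it.
- **Consent.** Whether main-trial consent covers this use cannot be settled from the documents available. This stands as a condition.

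**Conclusion.** The point holds as a missed efficiency. It is not an error: the stated event counts reproduce. For a model limited to demographics, clinical data and radiographic parameters, validation in the KJD patients outside the substudy would reduce the 95% half-width of the AUC from about 0.13–0.15 to about 0.05–0.06 (0.055–0.064 in 340 patients after 15% loss). It would also free all 200 substudy patients for development. Because the substudy runs in a selection of the 14 centres, the validation set would come partly from other centres, which is closer to external validation than a held-out third of the same sample.

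It would be too strong to say that 66 patients cannot show whether the scores predict response at all. At the assumed AUC of 0.70 the lower limit is 0.555 to 0.574, which excludes 0.50. The fair statement is that an interval running from roughly 0.56 to 0.84 does not allow a judgement of clinical usefulness.

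The result rests on the assumed AUC, the protocol's 30% to 50% response range applying outside the substudy as well, scheduled data being obtained, and consent. Priority is low: this is a substudy objective, listed among the secondary objectives in section 2.

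**What to change.** In sections 4.4 and 10.3, state that the model limited to demographics, clinical data and radiographic bone parameters (KOALA, KIDA) will be developed in the substudy patients and validated in the KJD patients outside the substudy. For that model, this replaces the random one-third split. Add the expected number of validation patients and events to 4.4.

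Keep the common sample of 200 for every step that adds MRI, CT, DEXA or biochemical markers, and for the comparison of added value over the radiographic model.

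Cost: protocol and SAP wording, automated scoring of about 400 existing baseline radiographs, and confirmation that main-trial consent covers this use. No additional patients, visits or imaging are needed. KIDA is already used on KJD radiographs for joint space width.
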